Neither the subject nor subject's insurance will be responsible for research related costs. Research related costs are specifically the use of the Proflavine and the use of the imaging probe which will be covered by the study. The actual screening endoscopy is standard of care (only patients previously scheduled for endoscopy are recruited). Thus, the costs related to the clinically indicated upper endoscopy are not research and are covered by the subject or their insurance.

In the event of an adverse event caused specifically by the use of the Proflavine or study device (marHRME), the subject will not be responsible for costs of care. If any standard of care injury is sustained (by standard of care endoscopy procedures), the costs of care will not be covered by the study.

If subjects will be paid (money, gift certificates, coupons, etc.) to participate in this research project, please note the total dollar amount (or dollar value amount) and distribution plan (one payment, pro-rated payment, paid upon completion, etc) of the payment.

Dollar Amount:

0

Distribution Plan:

Subjects will not be paid to participate in this research project.

Section M: Genetics

How would you classify your genetic study?

Discuss the potential for psychological, social, and/or physical harm subsequent to participation in this research. Please discuss, considering the following areas: risks to privacy, confidentiality, insurability, employability, immigration status, paternity status, educational opportunities, or social stigma.

There is no genetic component to this study.

Will subjects be offered any type of genetic education or counseling, and if so, who will provide the education or counseling and under what conditions will it be provided? If there is the possibility that a family's pedigree will be presented or published, please describe how you will protect family member's confidentiality?

Section N: Sample Collection

SAMPLE: Tissue

What is the purpose of the sample collection?

Tissue obtained by biopsy will be collected for clinical diagnosis. No tissue or samples are collected only for research. The slides/tissue blocks used for a clinical diagnosis will be available for re-review by the pathologists to confirm a final study diagnosis.

For blood draws, specify the amount drawn, in teaspoons, at each visit and across the course of the subjects entire participation time.

n/a

Is there the possibility that cell lines will be developed with this sample?No

Sample will be obtained from:

Pathology

Will the sample be stripped of identifiers?

No

If sample will be released outside the hospital:

Will sample be released to anyone not listed as an investigator on the protocol? Will the information be identifiable, coded or

de-identified?

Slides will be removed of identifiers and coded and sent to the pathologists on protocol

Will sample material be sold or transferred to any third parties? Will the information be de-identified?

Only coded information will be shared with investigators on the protocol.

If sample will be banked for future use:

Where will the sample be banked and for how long?

No

Does the banking institution have an approved policy for the distribution of samples?

n/a

If the entire sample will NOT be used during the course of this research study:

Will the remaining tissue be discarded? If not what will be done with the remaining sample after study completion and how long will the sample be kept?

n/a

Will samples be made available to the research subject (or his/her medical doctor) for other testing?

No

If a subject withdraws from the study:

Will subject have the option to get the remaining portion of their sample back?

No

Will samples be destroyed? If not, will they be kept anonymously? What will happen to the sample if the subject revokes authorization?

n/a

Will data obtained from their sample be deleted? What will happen to the sample if the subject revokes authorization?

n/a

Will study data or test results be recorded in the subject's medical records?

No

Will results of specific tests and/or results of the overall study be revealed to the research subject and or his/her doctor?

n/a

Please identify all third parties, including the subject's physician, to receive the test results.

n/a

Section O: Drug Studies

Does the research involve the use of ANY drug* or biologic? (*A drug is defined as any substance that is used to elicit a pharmacologic or physiologic response whether it is for treatment or diagnostic purposes)

Yes

Does the research involve the use of ANY gene transfer agent for human gene transfer research?

No

O1. Current Drugs

[Drug : Proflavine Hemisulfate](#)

Is this study placebo-controlled?

No

Will the research involve a radioactive drug?

No

Section P: Device Studies

Does this research study involve the use of ANY device?

Yes

[Device 1: HRME](#)

Section Q. Consent Form(s)

None

Section R: Advertisements

None

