This is a single-arm feasibility study and the clinical procedure will not be performed at Baylor. Baylor is coordinating center and will receive the data and monitor/coordinate the study. The actual feasibility study (n=50) will be conducted at the University of Sao Paolo, Brazil under the local PI, [name]. [name] (Baylor) is the coordinating PI for the overall grant though this pilot project will occur solely in Brazil.

Baylor will travel to USP to initiate the study and provide training on data collection, use and storage of the drug and device, and study procedures. Baylor will oversee the initiation of the feasibility study and the first 25 cases to ensure valid data collection. Baylor will communicate monthly (or more often as needed) with USP research team to answer questions and monitor data collection procedures. Baylor will travel yearly to monitor progress and at the end of the study close-out procedures.

Patients undergoing endoscopy for ESCN screening (n=50) at USP will be recruited by [name] and his team for the study. All study subjects will receive White Light Imaging and Lugol's Chromoendoscopy (LCE) which is the current standard of care procedure. We will record any LCE abnormal (suspicious) areas and record the clinician's plan of action (Biopsy vs. No Biopsy vs. Treat). Following LCE, all subjects will receive Mobile, Augmented Reality High Resolution Microendoscope (marHRME) imaging with the study contrast agent (Proflavine) of any LCE-identified abnormal areas as well as LCE normal areas (1:4 ratio abnormal to normal). We will record the subjective clinician read and confidence level in their diagnosis (high, low), and their plan of action (Biopsy vs. No Biopsy vs. Treat). Then we will image the same abnormal and normal areas with the marHRME and record the software read, clinician confidence level, and plan of action. Finally, the imaged areas will be biopsied or resected and evaluated by a pathologist. All subjects will receive both standard of care and marHRME imaging.

Once data is collected at USP, data will be removed of identifiers and coded and will be transferred to BCM. BCM will be responsible for data entry, management, and analysis.

Inclusion Criteria:

Outpatients undergoing routine (standard of care) Lugol's chromoendoscopic screening for squamous cell neoplasia will be eligible for enrollment including patients with known history of head/neck squamous cell cancer.

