Patients must be >18 years old and able to give informed consent.

For the provider surveys and interviews, all providers (clinicians, trainees) who are working on the project will be eligible to participate. There is no obligation to participate in the study and this will be explained via the research letter included in Section S.

Exclusion Criteria:

- Allergy or prior reaction to the fluorescent contrast agent proflavine - Patients who are unable to give informed consent - known advanced squamous cell carcinoma of the distal esophagus, or dysplastic/suspected malignant esophageal lesion greater than or equal to 2cm in size not amenable to endoscopic therapy - Patient unable to undergo routine endoscopy with biopsy: - women who are pregnant or breastfeeding - prothrombin time greater than 50% of control; PTT greater than 50 sec, or INR greater than 2.0 - inability to tolerate sedated upper endoscopy due to cardio-pulmonary instability or other significant medical issues

For the provider surveys and interviews, all providers (clinicians, trainees) who are working on the project will be eligible to participate. There is no obligation to participate in the study and this will be explained via the research letter included in Section S. Providers will be excluded if they decline participation or otherwise opt out of the proposed research project.

F2. Procedure

[name] will accrue subjects (n=50) already scheduled for endoscopic screening due to a high risk for ESCC (head and neck cancer history; heavy smoking and alcohol, other dietary or geographic risk factors). Lugol's chromoendoscopy (LCE) is the current standard of care for esophageal cancer screening.

To uphold this standard of care and recruit patients already scheduled for endoscopy, LCE will be performed on all patients, followed by marHRME of Lugol's voiding (unstained areas). Subjects will be sedated per standard protocol (IV sedation) and undergo white-light endoscopy with application of Lugol's iodine. In each subject, the location of each Lugol's unstained area (level, quadrant) will be recorded and digital images obtained. The endoscopist's clinical impression will be recorded for each Lugol's abnormal area and visible lesions ('non-neoplastic' vs. 'neoplastic') as well as his/her proposed plan: a. no biopsy, b. biopsy, c. endoscopic treatment.

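### The prothrombin-time exclusion, as written, is met by a normal value; it should read more than 50% above control, with the unit stated (minor correction)

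*Combined protocol and SAP*

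**What the plan says.** The exclusion criteria in section F1 (Design) of the combined protocol and SAP give three clotting limits in one item: "prothrombin time greater than 50% of control; PTT greater than 50 sec, or INR greater than 2.0". A few items earlier in the same list stands "Patient unable to undergo routine endoscopy with biopsy". It ends in a colon and appears to head the pregnancy, clotting and cardio-pulmonary items, although the layout of the list is lost in the extracted text.

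The inclusion criteria in the same section describe the intended population: "Outpatients undergoing routine (standard of care) Lugol's chromoendoscopic screening for squamous cell neoplasia will be eligible for enrollment".

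No other section restates the PT limit, gives its unit or defines the control.

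**The concern.** The PT limit compares the patient's value with half of control. A normal value is about equal to control, so it lies well above that limit and triggers the exclusion. Followed to the letter, the rule removes the routine screening outpatients whom the inclusion criteria invite, unless their PT happens to be at or below half of control.

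At stake is whether an operative eligibility rule can be applied and monitored as it stands. If the site enrols patients with a normal PT, as it surely should, each of those enrolments departs from the written criterion, and a monitor must either record a deviation or overlook it.

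**Working it through.** The plan gives no calculation on this point to reproduce. The check is to apply the criterion literally and compare it with its neighbours.

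**Inputs from the document (section F1).**
- PT limit: "prothrombin time greater than 50% of control", with no unit.
- Companion limits: "PTT greater than 50 sec, or INR greater than 2.0". Each has a clear scale, and each excludes abnormally high values, that is, slow clotting.

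**Assumed, because the document does not give them.**
- Control PT, C: 10 to 15 seconds.
- International sensitivity index (ISI) of the PT reagent: 1.0 to 1.7.

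**Step 1. A normal value under the literal rule.** For a patient at control, PT/C = 1.00 = 100%. The rule excludes if PT/C > 0.50. Since 1.00 > 0.50, the patient is excluded, whatever the value of C. A reading in percent activity gives the same answer: normal is about 100%, and 100% > 50%.

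**Step 2. Do the other limits rescue the patient?** No. The three limits are alternatives, so meeting any one excludes. A normal PTT and a normal INR leave the PT exclusion in force.

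**Step 3. Written and likely intended cut-offs, PT in seconds.** Written: 0.5 × C. Likely intended (more than 50% above control): 1.5 × C. Their ratio is 1.5 / 0.5 = 3.

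| Assumed control C (sec) | Written cut-off 0.5C (sec) | Likely intended cut-off 1.5C (sec) |
|---|---|---|
| 10 | 5.0 | 15.0 |
| 12 | 6.0 | 18.0 |
| 15 | 7.5 | 22.5 |

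A normal PT, close to C, lies between the two. It is excluded by the written cut-off and passes the likely intended one. A PT above 1.5C exceeds both, so in seconds the written rule excludes too many patients and misses none with a prolonged PT.

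**Step 4. Could the PT limit simply be dropped?** INR = (PT ratio)^ISI, taking the control as the reference PT for the INR. At the likely intended limit of 1.5:
- ISI 1.0: 1.5^1.0 = 1.50
- ISI 1.2: 1.5^1.2 = 1.63
- ISI 1.4: 1.5^1.4 = 1.76
- ISI 1.71: 1.5^1.71 = 2.00

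The two limits coincide at ISI = ln 2 / ln 1.5 = 1.71. Below that, some patients exceed the PT limit without reaching INR 2.0. With ISI 1.0, these are the patients with a ratio above 1.5 and up to 2.0. The PT limit is therefore not redundant over most of the assumed range.

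**The case against.** The strongest reply is that this is a slip of wording with almost no consequence. An endoscopist will read the phrase as shorthand for prolonged by more than 50%. The item is a time, the comparison is upward, and the adjacent PTT limit is in seconds. A patient with normal clotting is plainly not someone who cannot have an endoscopy with biopsies, so the apparent parent item argues against literal use. A literal reading would also stop accrual almost at once and so reveal itself. All of this stands as an argument about weight. It does not make the written limit right.

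Three stronger readings are tempting, and the documents do not support them.

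- *The rule lets patients with impaired clotting through.* If PT were reported as percent activity, the written direction would be reversed: 100% would be excluded and 40% would pass. But the document never mentions percent activity, and the wording fits a time. Even then, the PTT and INR limits would remain. This possibility is a reason to state the unit, not evidence of a safety failure.
- *Oversight ends halfway, so the error could run on.* Section F1 has the coordinating center oversee the first 25 of 50 cases, but it also provides for at least monthly communication and yearly monitoring visits. Section H3 adds an initiation visit before enrolment and an external monitor. None of this text names eligibility limits, but oversight does not stop at case 25.
- *The trial will exclude nearly everyone.* That follows from the letter of the rule, but the intent is evident and the site would probably apply it.

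**Conclusion.** The concern holds as a minor correction: the PT exclusion is wrong as written. That a normal value meets it follows from the text alone and does not depend on the assumed control. The written cut-off is one third of the likely intended one. That comparison assumes that more than 50% above control was meant, which the companion limits support but no sentence confirms.

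The practical effect is probably small, and the number of the 50 subjects affected cannot be derived from the documents. The sample size and power statement in section G1 rests on 50 subjects, accuracies of 80% and 45%, and a discordant proportion of 0.7. No clotting limit enters it, or the McNemar comparison of accuracy in section G2. A reader should not infer a threat to the primary result.

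**What to change.** Replace the PT limit with: *PT more than 50% above control (PT/control ratio >1.5)*, and state the unit in which the site reports PT. If its laboratory reports percent activity, use the corresponding limit, *PT activity less than 50%*. Leave the PTT and INR limits as they are.

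Keep the PT limit rather than deleting it. As Step 4 shows, leaving its role to INR >2.0 could loosen the bleeding screen before biopsy or resection.

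The cost is a one-line protocol correction and a check of the reporting unit with the site's laboratory. Sample size, procedures and analysis do not change.

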
Section D: Purpose and Objectives

We have a current trial in China and the US which provides significant support for the safety, cost-effectiveness, accuracy and efficiency of a high resolution microendoscope (HRME)-guided approach in the hands of experienced clinicians. To improve functionality, portability and broader use of this device by non-experts, we recently developed a prototype marHRME platform with an automated, augmented reality (AR)-interpretation that provides an overlaid endoscopic + micro-endoscopic view, facilitating diagnosis and biopsy targeting. Our hypothesis is that this mobile device with automated, AR optical biopsy diagnoses can efficiently and accurately facilitate endoscopic cancer detection in LMICs with less experienced providers and is acceptable to providers and patients. Objective 1: Our first objective is to evaluate the marHRME technology in terms of performance, efficiency, and impact. In a single-arm, feasibility study (n=50) of high-risk subjects undergoing Lugol's chromoendoscopy (LCE) followed by marHRME for ESCN screening, we will evaluate the diagnostic performance and efficiency of this automated optical biopsy device. Our main hypothesis is that the marHRME will (1) increase the accuracy of Lugol's endoscopy (LCE), other exploratory hypotheses are (2) increase the accuracy of marHRME among novices and be non-inferior to experts, (3) increase user confidence among experts and novices and, subsequently, (4) increase the efficiency and impact of LCE by reducing biopsies and second procedures. For performance for marHRME vs. Standard of Care, we will compare the accuracy of the marHRME + LCE vs. LCE alone to the gold-standard histopathology (expert GI pathologist). For performance of the Machine vs. Man, we will compare accuracy of the marHRME software read to novice and expert clinicians' subjective read to gold-standard histopathology. For clinician confidence and clinical impact, we will determine the clinician's confidence level in the software diagnosis and the potential clinical impact of this diagnosis among novice and expert endoscopists using marHRME. Clinical impact will be determined by whether the marHRME diagnosis alters the clinician's decision at the point-of-care to biopsy vs. not biopsy vs. treat the visualized site. For efficiency (biopsy saving and diagnostic yield), we will determine the number of patients who are spared any biopsy due to marHRME. We will compare the diagnostic yield of marHRME+LCE vs. LCE alone (diagnostic yield= neoplastic biopsies/total number of biopsies obtained in biopsied patients). Objective 2: Our secondary objective is to evaluate the acceptability of the technology among patients and providers. All patients participating in the study will be invited to participate in a brief (20 min) interviewer-administered survey prior to undergoing endoscopy to assess attitudes and barriers to marHRME (T1), and a follow-up interview (7 days post-procedure) to determine experiences and acceptability (T2). Informed consent and the initial interview will be conducted in a private clinic room by trained study staff from the Brazilian team using a brief Portuguese-language survey. The follow-up interview will occur by phone, after a routine follow-up call by clinical staff. The endoscopists and trainees participating in the feasibility study will be invited to participate in a series of questionnaires and in-depth interviews administered at different time points of the study to assess provider acceptance. Informed consent will be obtained prior to the first interview. Clinicians will answer a brief questionnaire to assess acceptance of marHRME prior to undergoing training (T1), after training (T2), and after conducting 25 procedures (T3). At T3, endoscopists and trainees will participate in a 30-minute semi-structured interview to assess marHRME experience. The interviews will be audio recorded, professionally transcribed, and

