Subsequently, marHRME will be performed of all Lugol's unstained (abnormal) sites prior to tissue biopsy. The endoscopist will activate the marHRME glasses and marHRME performed: (1) 1-10 ml proflavine hemisulfate (0.01%) will be sprayed on the esophageal mucosa, (2) the marHRME probe placed gently on the Lugol's abnormal areas, (3) the 'optical biopsy' image will be displayed on the AR glasses (endoscopic image will remain displayed on the standard monitor behind it). (Proflavine is used under an IND #102217).

The endoscopist will FIRST make a subjective interpretation ('non-neoplastic' vs. 'neoplastic'), record their confidence level in the diagnosis (high confidence vs. low confidence), and indicate their plan of action (a. biopsy, b. no biopsy, c. treat). All of this will be done WITHOUT the image-analysis software.

Once this qualitative read is recorded, the image analysis software will be turned on (foot pedal) and the software diagnosis provided in real-time with display on the AR glasses. The quantitative ("Machine") read will be recorded, the confidence level of the endoscopist obtained again, and the (revised) plan of action recorded (a numerical score). The software output (score) will be determined neoplastic (cancer) or non-neoplastic (normal) based on a predetermined

algorithm threshold. This quantitative read may influence clinician read, plan, and confidence.

The HRME procedure (including "man" and "machine" reads), standard endoscopy and biopsy time will be recorded. The research coordinators will indicate the biopsy number/location on an esophageal map diagram. The biopsies from each site will be placed in formalin per standard-of-care and labeled according to biopsy location (quadrant: 12, 3, 6, 9 o'clock).

In all subjects, all Lugol's abnormal areas will be biopsied (to uphold the standard of care); however, HRME "non-neoplastic" sites will be considered not tissue-biopsied for purpose of the analysis. All biopsies will be submitted for consensus diagnosis by an expert GI pathologist. All patient adverse events (bleeding, infection, perforation) that occur within 7 days after the procedure will be recorded on follow up call.

It is very possible that the HRME will increase the accuracy of standard Lugol's screening and may reduce unnecessary biopsies by improving specificity. With novices, the HRME + computer algorithms may be very likely to improve accuracy and performance, based on our preliminary data from China.

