Expert clinicians will be defined as any clinician with prior microendoscopy experience (>25 procedures) and novices are clinicians without any prior experience. We will collect this information in the CRF and compare outcomes between the 2 groups of clinicians. The clinician will give a \checkmark read \checkmark (Neoplastic/Non neoplastic) and \checkmark plan \checkmark (Biopsy/No Biopsy/Ablate/ESD/EMR) at several timepoints: 1- Based solely on Lugol's (SOC), 2- Using HRME with no software (Qualitative Read), and 3- After software overlay (Quantitative Read). The marHRME output is a numerical score (quantitative). Based on this score, clinicians may change their plan for the lesion. For ex: if they read the image without the overlay and aren't sure if they should biopsy, a high (neoplastic) score may increase confidence in their decision to biopsy, or a low (non-neoplastic) score may increase confidence to not biopsy the area.

Section G: Sample Size/Data Analysis

G1. Sample Size

How many subjects (or specimens, or charts) will be used in this study?

Local: 0 Worldwide: 50

Please indicate why you chose the sample size proposed:

We will collect an average of 2-3 biopsies/subject in screening patients. All patients will have biopsies and their pathological diagnosis will be used to measure the accuracy of LCE and marHRME (man and machine). As mentioned, LCE has a sensitivity of > 95% but a specificity of <65% due to a high-false positive rate (82%) resulting in a low diagnostic yield (unnecessary benign biopsies) and, subsequently, increased cost. Our hypothesis is that the addition of marHRME to LCE will increase the accuracy, efficiency of marHRME, and clinical impact, particularly for novice endoscopists while increasing confidence levels in novice and experts. Based on the preliminary data, the accuracy of marHRME vs LCE was 83% (CI: 76-89%) vs 47% (CI: 39-55%). A sample size of 50 subjects will provide 87% power to detect a 35 % improvement in accuracy (80% for marHRME vs 45% for LCE) with a 5% two-sided significance level and 0.7 discordant pairs using McNemar's test for the paired data.

G2. Data Analysis

Provide a description of your plan for data analysis. State the types of comparisons you plan (e.g. comparison of means, comparison of proportions, regressions, analysis of variance). Which is the PRIMARY comparison/analysis? How will the analyses proposed relate to the primary purposes of your study?

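### Patients 'spared any biopsy' (exploratory) are counted without regard to histology, so the planned outputs do not separate correct sparing from missed neoplasia

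*Combined protocol and SAP*

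**What the plan says.** Section D lists, among its exploratory hypotheses, that marHRME will "increase the efficiency and impact of LCE by reducing biopsies and second procedures". Its measure is stated there: "we will determine the number of patients who are spared any biopsy due to marHRME". The companion measure is diagnostic yield: "diagnostic yield= neoplastic biopsies/total number of biopsies obtained in biopsied patients". G2 adds only that both are given as proportions with 95% confidence intervals.

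F2 has every Lugol's-abnormal area biopsied, but HRME non-neoplastic "sites will be considered not tissue-biopsied for purpose of the analysis". The rule names neither the analysis it governs nor the read that makes a site non-neoplastic. The same section provides histology for each biopsied site: "All biopsies will be submitted for consensus diagnosis by an expert GI pathologist". G1 says of the biopsies that "their pathological diagnosis will be used to measure the accuracy of LCE and marHRME (man and machine").

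On reads, F2 first takes the endoscopist's HRME interpretation without software. Then the software "read will be recorded, the confidence level of the endoscopist obtained again", together with a revised plan. The end of F2 says the clinician gives a read and a plan at three timepoints, the last two being "2- Using HRME with no software (Qualitative Read), and 3- After software overlay (Quantitative Read").

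**The concern.** F2 hopes to cut unnecessary biopsies through better specificity, and G1 identifies the unnecessary ones as benign. A biopsy avoided in a patient with neoplasia is not a gain of that kind, yet the measure as written counts it as one. With false positives held fixed, a missed neoplastic site can never lower the spared count, and it raises the count whenever it removes a patient's last HRME-positive site. A less sensitive read can therefore look more efficient. This figure would support any later claim that biopsies can be skipped, so a reader needs to know how many of the spared patients had disease.

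The basis for calling a site spared matters too. F2 says the software read may influence the clinician's read, plan and confidence, so the candidate bases can disagree and give different counts. Unless one is named beforehand, the choice could follow the results.

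**Working it through.** **The plan's own figures.** The documents give no expected number of spared patients, so there is none to reproduce. The planning values borrowed below (G1: accuracy 80% vs 45%, discordant proportion 0.7, n = 50, two-sided 5%) do reproduce the stated 87% power: Φ[(0.35·√50 − 1.96·√0.7)/√(0.7 − 0.35²)] = Φ(1.10) = 86.4%, and enumerating the uncorrected McNemar test gives 87.0%. That figure is not in dispute.

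**Assumptions (mine, for illustration).** Only Lugol's-abnormal sites are analysed. LCE calls each one positive; this simplifies, since F2 also allows a non-neoplastic impression. There are two sites per patient; G1 gives 2-3 biopsies per subject, not sites.

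**Set A, G1 planning values applied to sites.** Neoplastic share π = 0.45.
- TN = (0.7 + 0.35)/2 = 0.525
- FN = (0.7 − 0.35)/2 = 0.175
- TP = 0.45 − 0.175 = 0.275
- FP = 1 − 0.525 − 0.175 − 0.275 = 0.025
- Sensitivity 0.275/0.45 = 61%; specificity 0.525/0.55 = 95.5%; NPV 0.525/0.70 = 75%

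**Set B, one reading of G1's 82% false-positive figure.** π = 0.18, accuracy 0.80, sensitivity assumed 0.90.
- TP = 0.162, FN = 0.018
- TN = 0.80 − 0.162 = 0.638, FP = 0.182

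**Formulas, 50 patients.**
- Sites independent: spared = 50(TN + FN)²; with missed neoplasia = 50[(TN + FN)² − TN²]
- Truth shared within patient, reads independent: spared = 50[π(1 − Se)² + (1 − π)Sp²]; with missed neoplasia = 50π(1 − Se)²

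| Scenario | Spared | With missed neoplasia | Share of spared |
|---|---|---|---|
| A, independent: 50·0.70²; 50(0.70² − 0.525²) | 24.5 | 10.7 | 44% |
| A, shared truth: 50(0.45·0.389² + 0.55·0.955²); 50·0.45·0.389² | 28.5 | 3.4 | 12% |
| B, independent: 50·0.656²; 50(0.656² − 0.638²) | 21.5 | 1.2 | 5.4% |
| B, shared truth | 24.9 | 0.1 | 0.4% |

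**Does NPV recover the count?** In set A, 25% of HRME-negative sites are neoplastic, but the share among spared patients is 44% or 12% depending on within-patient dependence. At the extremes, pairing every FN site with a TP site gives 0 incorrectly spared patients. Pairing every FN site with a TN site gives 50·2·0.175 = 17.5. An NPV of 75% fits both. For set B the bounds are 0 and 50·2·0.018 = 1.8.

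**Does diagnostic yield show it?** In set A, yield is 0.275/0.300 = 91.7%. With no misses and the same false positives it would be 0.45/0.475 = 94.7%. Missing 39% of neoplastic sites costs three points of yield, against 45% for LCE. A wholly spared patient contributes no counted biopsy to either part of the marHRME ratio.

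**The case against.** The strongest reply is that this is an exploratory count in a self-described pilot, reported with a confidence interval and no planned test. Sensitivity and NPV with intervals stand beside it, and a raw count of biopsies avoided is a legitimate efficiency measure in that company. The split could also be tabulated at any time, since sites are mapped, biopsies are labelled by location and pathology exists for each. All of that is fair. It limits the weight of the point, but it does not supply the patient-level number, which is absent from the listed outputs.

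The larger figures above deserve little reliance. Set A treats sample-size parameters as site-level truth with LCE positive everywhere, which implies 0% LCE specificity and 61% marHRME sensitivity. The documents state neither. F1 also describes imaging and biopsying LCE-normal areas while F2 confines biopsy to abnormal ones, so the set of analysed sites is itself unsettled.

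Some stronger readings are tempting but unsupported:
- **Every patient whose neoplastic sites were all missed counts as spared.** Not so: one benign site read neoplastic keeps that patient out of the count.
- **Diagnostic yield is blind to misses.** It falls with them, though only slightly in the set A example.
- **The F2 rule distorts the primary accuracy comparison.** Section D, G1 and G2 tie accuracy to histology, so the rule is evidently meant for saving and yield.
- **Three distinct reads are certainly recorded.** F2 uses the term quantitative for the machine read, and later for a read the clinician gives after overlay. Whether a separate post-overlay clinician read exists is unclear.

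**Conclusion.** The point holds as a modest improvement to an exploratory endpoint. Followed exactly, the plan counts a patient as spared when every analysed site is read HRME non-neoplastic, whatever the histology, and no listed output says how many such patients had neoplasia. The size could be negligible or substantial: about 0.1 to 10.7 of 50 patients across the four scenarios, with bounds of 0 to 17.5 under set A and 0 to 1.8 under set B. All of these rest on assumed site numbers, prevalence and within-patient dependence. The conclusion does not depend on which scenario applies, because the planned summaries would not reveal it.

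A reader might infer harm to participants or a flaw in the primary endpoint. Neither follows: every Lugol's-abnormal area is biopsied, and accuracy is judged against that pathology.

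**What to change.** In G2, report patients spared any biopsy in two rows: correctly spared (all biopsied sites benign on histology) and incorrectly spared (at least one neoplastic site). Give each a binomial 95% confidence interval, and take the correctly spared proportion as the measure of benefit.

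With that change, add two sentences to F2 or G2. One should state that the rule treating HRME non-neoplastic sites as not biopsied applies only to biopsy saving and diagnostic yield. The other should prespecify the single recorded basis that makes a site spared: the HRME read without software, the software read, or the post-overlay read or plan.

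The cost is wording and one table; F2 already sends every biopsy to pathology, so no new data are needed. The saving will look less favourable, and the interval on incorrectly spared patients will be wide: 3 of 28 spared, for example, has an exact 95% interval of 2% to 28%.
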